### **4.3. Exposure to Study Drug**

#### **4.3.1. Extent of Exposure and Treatment Compliance**

Subjects were trained by study personnel on how to self-administer study drug with the abaloparatide-SC injection pen or the abaloparatide-sMTS patch. On the days of study site visits, study drug must be administered at the study site to accommodate pre-administration and post-administration procedures.

The overall duration of study drug exposure will be calculated using the data recorded on the eCRF as follows:

- Overall duration of study drug exposure (days) = (date of last dose – date of first dose) + 1.

If the date of last dose is missing, then the earlier of the following 2 dates will be used as the last dose date for analysis and summary purposes: the final visit/early termination visit date or the last drug dispense date + 30 days.

For the abaloparatide-SC group, the total number of doses delivered and study drug administration compliance will be calculated in two ways as follows:

- **Based on missed doses in subject diary:**
  - Number of doses delivered = Overall duration of study drug exposure – Total number of missed doses per subject diary
  - Percent compliance (%) to study drug administration =  $(\text{Number of doses delivered} / \text{Overall duration of study drug exposure}) \times 100\%$
- **Based on measurement of drug remaining in pen:**
  - Number of doses delivered =  $[(45.5 \text{ mm} \times \text{Number of used pens}) - \text{Sum of measurements of drug remaining in all used pens}] / 1.08 \text{ mm}$ . Here the 45.5mm is the initial measurement of unused study drug in an unused injection pen and 1.08mm is the distance the plunger travels for each 80 ug dose from the pen.

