Two different patches will be dispensed to subjects in the abaloparatide-sMTS group. The ultra-low bioburden patches will be dispensed from Day 1 to all subjects. Sterile patches (the patches intended for commercial use) will be dispensed to subjects after confirmation that the sterile product is bioequivalent to the ultra-low bioburden product (Study 058-05-023). For the abaloparatide-sMTS group, the duration of study drug exposure, duration category in months, number of doses delivered and percent compliance with study drug administration using two calculations of percent compliance will also be summarized by patch type (ultra-low bioburden, sterile) for the Safety, mITT and PP populations.

If a subject is shown to be  $<80\%$  compliant with study drug administration using both calculations of study drug administration compliance for abaloparatide-sMTS group, or is  $<80\%$  compliant with study drug administration using both calculations of study drug administration compliance for the abaloparatide-SC group, this subject will be considered as having a critical protocol deviation and thus excluded from the PP Population.

Subjects' drug exposure and compliance will be carefully reviewed against the onset of the COVID-19 pandemic. Each subject's study drug exposure and compliance prior to 01 March 2020 and on or after 01 March 2020 will be calculated based on information collected from the subject diary:

- For subjects with last dose date prior to 01 March 2020 and subjects with first dose date on or after 01 March 2020, their duration of study drug exposure (days), number of doses delivered, and percent compliance to study drug administration relative to 01 March 2020 will be calculated as above based on the missed doses in subject diary
- For subjects who started taking the study drug prior to 01 March 2020 and continued on or after 01 March 2020, their duration of study drug exposure and compliance before 01 March 2020 and on or after 01 March 2020 will be calculated as follow:
  - Durations of study drug exposure relative to 01 March 2020:
    - Duration before 01 March 2020 = 29 February 2020 – date of first dose + 1
    - Duration on or after 01 March 2020 = Overall duration of study drug exposure – duration before 01 March 2020; where overall duration of study drug exposure = last dose date – first dose date + 1

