The study drug exposure and percent compliance to study drug administration before 01 March 2020 and on or after 01 March 2020 will be summarized by treatment group for the Safety, mITT and PP populations. Similar summaries will not be provided by patch type (ultra-low bioburden, sterile) since the switch from ultra-low bioburden patch to sterile patch for subjects in abaloparatide- sMTS group did not occur until after 01 March 2020.

The number (%) of subjects with any missed dose or dose interruption as recorded on the Dose Interruption Log eCRF will be summarized by treatment group, along with the reason(s) for missed/interrupted dose(s) for the mITT, PP, and Safety populations. If a subject reported a start date for the missed/interrupted dose but no corresponding start date for the resumption of study drug, the occurrence of the missed dose/dose interruption will not be included in the summary. The total number of days with missed/interrupted dose for each subject will be calculated and summarized by descriptive statistics and in the following categories: 1-7 days, 8-14 days, 15-28 days, >28 days by treatment group.

Study drug exposure and study drug administration compliance data will be listed by treatment (including patch type for abaloparatide-sMTS group), study site, and subject number.

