### **4.6.1. Adverse Events**

All AEs will be coded to SOC and PT using MedDRA Version 24.0.

Analyses of AEs will be performed for those events that are considered to be TEAEs. A TEAE is defined as any AE that was absent (i.e., had not occurred) or had resolved prior to the start of study drug, and which occurred on or after the date of the first dose of study drug and within 30 days of the last dose of study drug; or any AE that started prior to the first dose of study drug, was ongoing after study treatment started, and increased in severity after the start of study drug and within 30 days of the last dose of study drug. AEs with missing onset dates will be handled according to the Conventions for Imputing Missing Dates in [Appendix A](#).

TEAEs reported as unanticipated adverse device effects (UADE) or medical device reports (MDR) are those AEs with “Yes” to all of the following three questions on the AE eCRF: “Serious Event?”, “Was AE related to device?”, and “Would you consider this AE unexpected?”. For North American sites, unanticipated device-related SAEs will be reported as UADE for abaloparatide-sMTS, and will be reported as MDR for subjects on abaloparatide-SC. For European sites, unanticipated device-related SAEs will be reported as UADE for subjects on either abaloparatide-sMTS or abaloparatide-SC.

In any tabulation of TEAEs, a subject contributes only once to the count for a given PT and/or SOC, or for a time period category. For summaries by severity, a subject with multiple occurrences of a TEAE will be represented under the most severe occurrence. For summaries by relationship to study drug, a subject with multiple occurrences of a TEAE will be represented under the most related occurrence.

An overall summary of AEs will be presented by treatment group and overall, including the number and percentage of subjects reporting AEs, TEAEs, study treatment-related TEAEs (with probable or possible relationship to study drug), severe TEAEs, treatment-related severe TEAEs, serious TEAEs, treatment-related serious TEAEs, TEAEs leading to study drug interruption, TEAEs leading to study drug withdrawal, TEAEs leading to discontinuation from study, TEAEs related to the device, and TEAEs resulting in death.

The following summaries will be presented:

- TEAEs by SOC and PT
- TEAEs by SOC, PT, and region (North America, Europe)
- TEAEs by SOC, PT and Maximum Severity (mild, moderate, or severe)

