All TEAE summaries, including AEs of special interest (AESI, [Section 4.6.2](#)) will be presented by patch type (ultra-low bioburden, sterile) for the abaloparatide-sMTS group. The exposure-adjusted incidence rate of TEAEs will also be presented by patch type for the abaloparatide-sMTS group. The exposure-adjusted incidence rate is calculated as number of subjects with TEAEs divided by the total on-treatment exposure in subject-years.

The number of subjects with any TEAEs, the number of subjects with any SAEs, and the number of subjects with TEAEs leading to study drug withdrawal will also be summarized by treatment group, SOC, PT and age group (< 65, 65 - < 75, and  $\geq$  75 years). Similar tables will be provided by treatment group, SOC, PT and BMI group (BMI < 25, 25  $\leq$  BMI < 30, BMI  $\geq$  30). Both summaries by age group and by BMI group will also be presented by patch type (ultra-low bioburden, sterile) for the abaloparatide-sMTS group.

By-subject listings will be provided for all AEs, including an indicator for TEAE/non-TEAE and for patch type (ultra-low bioburden, sterile). Listings will also be provided for deaths, serious TEAEs, TEAEs leading to study drug withdrawal, TEAEs leading to discontinuation from study, AEs of special interest, and severe AEs.

A data listing for COVID-19 related AEs (AE PTs related to COVID-19 using MedDRA Version 24.0) will be prepared by SOC and PT. A listing of subjects who experience an UADE or MDR will be provided from the clinical database.

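### The exposure-adjusted TEAE rate by patch type counts events up to 30 days after the last dose but divides by on-treatment time only, which inflates the rate for whichever patch a woman wore last

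*SAP*

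**What the plan says.** SAP 4.6.1 (Adverse Events) announces the summary: "The exposure-adjusted incidence rate of TEAEs will also be presented by patch type for the abaloparatide-sMTS group". It then gives the formula: "The exposure-adjusted incidence rate is calculated as number of subjects with TEAEs divided by the total on-treatment exposure in subject-years".

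The same section sets the TEAE window. For a new event, it covers an AE "which occurred on or after the date of the first dose of study drug and within 30 days of the last dose of study drug". Footnote 18 to SAP Table 1 collects AEs over the same 30 days, so such events will be in the database.

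Exposure time is defined once, in SAP 4.3.1: "Overall duration of study drug exposure (days) = (date of last dose – date of first dose) + 1". That section also plans exposure summaries by patch type, but gives no separate start and stop rule for each patch.

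The order of patches is fixed. SAP 4.3.1 says "The ultra-low bioburden patches will be dispensed from Day 1 to all subjects", and later "Sterile patches (the patches intended for commercial use) will be dispensed to subjects after confirmation that the sterile product is bioequivalent". The change of patch "did not occur until after 01 March 2020". The SAP gives no switch date, no number of switchers and no duration on sterile patches.

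SAP 4.6.1 lists a patch-type indicator in the AE listings. It has no rule for assigning a TEAE to a patch type around the switch or after the last dose.

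**The concern.** An exposure-adjusted rate exists to make periods of unequal length comparable. That works only if events and time at risk are counted over the same window. Here up to 30 days of events per woman enter the numerator with no matching time below.

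The extra days do not fall evenly. A switcher's ultra-low bioburden period ends when she moves to sterile patches, so under attribution to the last patch her post-treatment month belongs to the sterile patch. A woman who never switches carries that month on ultra-low bioburden. The shorter the time on the last patch, the larger the proportional effect. Two patches with the same true hazard could therefore show different rates, and one of them is the patch intended for commercial use.

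**Working it through.** The documents state no exposure-adjusted rate, so there is no planned figure to reproduce.

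**Inputs from the SAP.** Post-dose window: 30 days (4.6.1). Exposure ends at the last dose (4.3.1). Planned treatment: 12 months of 30 days, that is 360 days (1.2.1). Each subject counts once per term (4.6.1).

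**Assumptions.** T is days on the last patch. r is the hazard after stopping divided by the hazard on treatment. Post-dose TEAEs go to the last patch. Every woman is followed for the full 30 days.

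**Step 1. Rare events.** Inflation factor = 1 + r × 30/T, which is (T+30)/T when r = 1.

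| T (days) | r = 1 | r = 0.5 |
|---|---|---|
| 60 | 1.50 | 1.25 |
| 90 | 1.33 | 1.17 |
| 180 | 1.17 | 1.08 |
| 270 | 1.11 | 1.06 |
| 360 | 1.08 | 1.04 |

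**Step 2. Each subject counted once.** With constant hazard L per year and r = 1, the factor is [1 − exp(−L(T+30)/365.25)] / [1 − exp(−LT/365.25)].

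| L per year | T = 90 | T = 180 | T = 360 |
|---|---|---|---|
| 0.05 | 1.331 | 1.164 | 1.081 |
| 1 | 1.282 | 1.124 | 1.047 |
| 2 | 1.238 | 1.090 | 1.025 |

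The excess shrinks as events become common, because more women have already been counted.

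**Step 3. Effect on the patch comparison, rare events, r = 1.** Let a share s switch, with 360 − T days on ultra-low bioburden and T on sterile. The rest stay on ultra-low bioburden for 360 days.

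- Sterile factor = (T+30)/T.
- Ultra-low bioburden factor = [s(360−T) + (1−s)390] / [s(360−T) + (1−s)360].
- At s = 0.5 and T = 90: 120/90 = 1.333, and 330/315 = 1.048. The sterile to ultra-low bioburden ratio is 1.333/1.048 = 1.27, although the true ratio is 1.
- For s from 0.25 to 0.75 and T from 60 to 180 days, that ratio runs from 1.09 to 1.47.

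More generally, take m switchers with U days on ultra-low bioburden and T on sterile, and n women who never switch, with V days each. Sterile inflation is 30/T and ultra-low bioburden inflation is 30n/(mU + nV). Sterile is inflated more when T < V + (m/n)U. The documents give none of these quantities.

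**Step 4. Does matching the windows suffice?** Take switchers with 270 days on ultra-low bioburden and 90 on sterile, and equal true hazards.

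| Sterile / ultra-low bioburden ratio | L = 0.05 | L = 2 |
|---|---|---|
| As planned | 1.35 | 1.87 |
| 30 days added to denominator | 1.01 | 1.40 |
| Only on-treatment onsets counted | 1.01 | 1.51 |

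For L = 2, ultra-low bioburden: [1 − exp(−2 × 270/365.25)]/(270/365.25) = 1.044 per year. Sterile as planned: [1 − exp(−2 × 120/365.25)]/(90/365.25) = 1.955. Sterile matched: the same numerator over 120/365.25 = 1.466. Then 1.955/1.044 = 1.87 and 1.466/1.044 = 1.40.

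The remaining excess arises because a woman counts once while her exposure keeps accruing after her first event, which lowers the rate for the longer-worn patch. If exposure over a period S stops at the first event, expected time at risk is (1 − exp(−LS))/L and the expected count is 1 − exp(−LS). Their ratio is L whatever the length of the period, so the bias goes.

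**The case against.** The strongest objection concerns attribution. The SAP has no rule tying a TEAE to a patch type. If the indicator means the patch in use at onset, post-dose events may belong to neither patch and the inflation disappears. If a 30-day window is run from the end of each patch, both rates are inflated. This stands: the size above is conditional on attribution to the last patch, which is the natural reading but is not written down.

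A reader might infer that the sterile rate must come out higher. The documents do not support that as a certainty. Women who stopped or finished before receiving sterile patches carry their post-dose month on ultra-low bioburden, and for early dropouts the proportional effect is large. The net direction depends on the condition in step 3.

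A reader might also take 33% as the expected bias. It requires 90 days on the last patch, a rare event and an unchanged hazard after stopping, none of which is stated. Application-site events are unlikely to begin without a patch. Protocol 6.6.3.2 ends daily self-assessment at Month 12 or EOT, and Protocol 6.2.8 lists no local-tolerance assessment, chemistry, serum calcium or urine collection at Visit 17. New findings of those kinds would seldom surface in that month. AE review is listed at that visit, however, so systemic and serious events can still enter the numerator.

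Finally, the rate is descriptive. SAP 4.6 plans no formal safety testing unless specified, none is specified here, and sterile patches follow a separate bioequivalence study. This limits the consequence, but it does not make the rate correct.

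**Conclusion.** The mismatch holds on the SAP's own wording: the numerator runs to 30 days after the last dose, the denominator does not, and nothing elsewhere aligns them. Reading on-treatment exposure to include a month off treatment would remove the problem, but the phrase does not allow it.

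Given attribution to the last patch, the rate for that patch is too high. With r = 1 and rare events the excess is 33%, 17% and 8% at 90, 180 and 360 days. At half the post-dose hazard it is 17%, 8% and 4%. At 2 events per year with r = 1 it is 24%, 9% and 2.5%. The sterile to ultra-low bioburden comparison is biased upward if time on sterile patches is the shorter, in the sense of step 3. The net size cannot be derived from the documents.

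The consequence is limited to a descriptive safety rate within the sMTS arm. The primary non-inferiority analysis, the comparison of sMTS with SC and the crude TEAE tables are unaffected. The correction is still worth making because it is nearly free.

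**What to change.** Amend the rate definition in SAP 4.6.1 in three respects.

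1. **Match the windows.** Either count only TEAEs with onset while that patch type is in use, or add the post-dose days (up to 30, ending at the last contact if earlier) to the denominator of the patch they follow.
2. **State the attribution rule.** Say which patch type receives a TEAE that starts around the switch, and which receives one that starts after the last dose.
3. **End exposure at the first event.** For each term, stop a subject's time at risk on a patch at her first such event on that patch. Matching the windows alone leaves a ratio of about 1.40 for common events in the example of step 4.

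The cost is a sentence or two in the SAP and a small programming change. The onset, dispensing and dosing dates it needs are already collected.

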#### **4.6.2. Adverse Events of Special Interest**

An adverse event of special interest (AESI) is an AE that is designated to be of special medical or scientific interest to the Sponsor. There are four major categories of AESIs as follows:

- Administration site reaction AEs -- Skin reaction AEs at the injection/application site
- Skin AESIs -- AEs of eschar, ulcer, or non-healing wounds at the injection/application site
- Hypersensitivity AESIs -- TEAEs in the Hypersensitivity Standardized MedDRA Query (SMQ narrow)
- Other AESIs:
  - Orthostatic hypotension
  - Tachycardia
  - Nausea
  - Hypercalcemia
  - Hypercalciuria
  - Hypophosphataemia

The MedDRA PTs, High Level Terms (HLT), and SMQs used to identify the AESIs are stored in the study folder in the Biometrics SAS environment.

An overall summary of the treatment emergent AESIs will be provided, in which the number of subjects with any adverse events, number of subjects with any TEAEs, number of subjects with any treatment-related TEAEs, number of subjects with any severe TEAEs, number of subjects with any treatment-related severe TEAEs, number of subjects with any serious TEAEs, number of subjects with any treatment-related serious TEAEs, number of subjects with any TEAEs leading to study drug withdrawal, number of subjects with any TEAEs leading to study drug interruption, number of subjects with any TEAEs leading to study discontinuation, number of subjects with any TEAEs related to the device, and number of subjects with any TEAEs leading to death will be summarized by treatment group and overall.

The treatment emergent AESIs will be summarized by PT and SOC for each of the AESIs. Summary of the onset time and duration of the treatment emergent AESIs will be provided by

treatment group using descriptive statistics (number of subjects, mean, SD, median, interquartile range, minimum and maximum).

AESI onset time groups include:

- 1 day
- 2-3 days
- 4-7 days
- 8-15 days
- 16-29 days
- 1 to <2 months
- 2 to <6 months
- 6 to <10 months
- $\geq$ 10 months

AESI duration groups include:

- For Administration site reaction AEs, Skin AESI and Hypersensitivity AESIs:
  - < 1 hour
  - 1-<2 hours
  - 2-<4 hours
  - 4-<24 hours
  - 1-<2 day
  - 2-3 days
  - 4-7 days
  - 8-15 days
  - 16-29 days
  - >29 days
- For other AESIs:
  - 1-<2 day
  - 2-3 days
  - 4-7 days
  - 8-15 days
  - 16-29 days
  - >29 days

For AESI duration, if there is more than one occurrence of the AESI for a subject, then the average duration for all occurrences for the subject will be used. If AE stop date is missing, then the last study date will be used. If both AE start date and AE stop date are missing, the AE duration will be missing.

To evaluate the relationship between AESIs and the antibody status, the incidence of treatment emergent AESIs will also be summarized by antibody status (ADA-, ADA+/Nab+, ADA+/Nab-, All ADA+, and Overall), SOC, and PT for both treatment groups.

An overall summary of the treatment emergent AESIs, as described above, will also be presented by treatment group (and overall) for the following subgroups:

- Age group (< 65, 65 - < 75, and  $\geq$  75 years)
- BMI group (BMI < 25,  $25 \leq$  BMI < 30, and BMI  $\geq$  30)
- Region (North America and Europe)

Subject listings will be provided for each of the AESIs.

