7.1.1. Adverse Events

An AE is any untoward medical occurrence in a clinical investigation subject administered a pharmaceutical product and that does not necessarily have a causal relationship with this treatment. An AE can therefore be any unfavorable and unintended sign (including an abnormal laboratory finding), symptom, or disease temporally associated with the use of a medicinal (investigational) product, whether or not related to the medicinal (investigational) product (International Conference on Harmonization [ICH], 1995).

AEs could include but are not limited to the following:

- Worsening (change in nature, severity, or frequency) of conditions present at the onset of the study
- Intercurrent illnesses
- Drug interactions
- Events related to or possibly related to concomitant medications
- Clinically significant abnormal laboratory values (this includes significant shifts from Baseline within the range of normal that the Investigator considers to be clinically important)
- Clinically significant abnormalities in physical examination, vital signs, and weight

 An abnormal laboratory value will not be assessed as an AE unless it requires a therapeutic intervention or is considered by the Investigator to be clinically significant

When possible, a clinical diagnosis for the study assessment should be provided rather than the abnormal test result alone (eg, urinary tract infection, anemia). In the absence of a diagnosis, the abnormal study assessment itself should be listed as the AE (eg, bacteria in urine or decreased hemoglobin).

Determination of clinical significance must be made by the Investigator.

All skin reactions at the application site reported by the subject and Investigator, expected or unexpected, and regardless of severity will be reported as AEs and should include reference to the application site. The Application Site Skin Adverse Event form should be completed and sent by the clinical site. Events of ulcer, eschars, and non-healing wounds at the application site will be evaluated as an AESI (Section 7.1.3.1). Skin AEs that occur at other locations of the body should be reported as AEs as appropriate, but are not to be recorded/entered using phrases such as 'at the application site', 'involving the application site', etc., to ensure the phrase 'application site' is used exclusively for the sites of study drug administration.

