7.1.4. Recording an Adverse Event

All AEs/SAEs will be entered into the electronic database.

Planned hospital admissions or surgical procedures for an illness or disease that existed before the subject was enrolled in the study are not to be considered AEs unless they occur at a time other than the planned date or the pre-existing illness or disease worsens after enrollment into the study.

Fractures identified during the study are not to be recorded as AEs unless the subject is hospitalized, the fracture is complicated, or the Investigator considers the fracture to be unrelated to the subject's underlying osteoporosis. All fractures will be identified and evaluated as part of the disease assessment and will be documented in the eCRF and by collection of source documents.

For both serious and non-serious AEs, the Investigator must determine the intensity of the event and the relationship of the event to study drug administration (abaloparatide-SC and abaloparatide-sMTS). Intensity for each AE will be defined according to the following criteria:

Intensity Definition

Mild Awareness of sign or symptom, but easily tolerated

Moderate Discomfort enough to cause interference with normal daily

activities

Severe Inability to perform normal daily activities

If the intensity of an adverse event changes within a day, the maximum intensity should be recorded. If the intensity changes over a longer period of time, the changes should be recorded as separate events (having separate onset and stop dates for each intensity).

Relationship to study drug or device, defined as study drug administration, will be determined by the Investigator according to the following criteria:

Relationship Definition

None No relationship between the event and the administration of study drug. The event is related to other etiologies, such as concomitant

medications or subject's clinical state.

Unlikely The current state of knowledge indicates that a relationship to study

drug administration is unlikely or the temporal relationship is such that

study drug administration would not have had any reasonable

association with the observed event.

Possible A reaction that follows a plausible temporal sequence from

administration of the study drug and follows a known response pattern to the suspected study drug. The reaction might have been produced by the subject's clinical state or other modes of therapy administered to the

subject.

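### AESI duration is averaged over adverse event records that the protocol splits when intensity changes, so one continuous reaction can be summarised as shorter than it was

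*SAP*

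**What the plan says.** **How events are recorded.** Protocol 7.1.4 has two rules for an event whose intensity changes. Within a day there is one record: "If the intensity of an adverse event changes within a day, the maximum intensity should be recorded". Over a longer period, "the changes should be recorded as separate events (having separate onset and stop dates for each intensity"). Protocol 7.1.1 brings skin reactions at the application site under these rules, since all of them, "expected or unexpected, and regardless of severity will be reported as AEs and should include reference to the application site".

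**How duration is summarised.** SAP 4.6.2 lists the AESI categories, among them "Administration site reaction AEs -- Skin reaction AEs at the injection/application site" and the skin AESIs (eschar, ulcer, non-healing wound). Onset time and duration are planned outputs by treatment group, with descriptive statistics and duration groups. The value per subject is set thus: "if there is more than one occurrence of the AESI for a subject, then the average duration for all occurrences for the subject". At the long end the groups are 2-3, 4-7, 8-15, 16-29 and >29 days.

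**What is not said.** The SAP does not define an occurrence. Nothing in SAP 4.6.1, 4.6.2, Section 5 or Appendix A links consecutive records of one event. The nearest guide is SAP 4.6.1, where "a subject with multiple occurrences of a TEAE will be represented under the most severe occurrence". There, occurrences of the same event can differ in severity, which fits a reading of one occurrence per record.

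**The concern.** Each rule is reasonable alone. Together they divide one continuous reaction into segments and then report the average segment. This happens with complete dates, so the SAP's rule for missing stop dates does not help.

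The shortening is selective. A reaction that stays at one intensity keeps its true length, while one that escalates or subsides over days is cut. Safety and tolerability of the patch are part of the study objective, and how long site reactions last is a natural question for it, above all for non-healing wounds. The duration table would understate the reactions a reader most wants to see.

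A second, smaller defect is that averaging produces fractions of a day, while the longer groups are written for whole days. A mean of 3.5, 7.5 or 15.5 days belongs to no group.

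**Working it through.** The plan states no figure to reproduce here, so the check applies its two rules to assumed reactions. The documents give neither the length of a reaction nor the number of intensity stages, and both are assumptions below.

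**One reaction.** Let a continuous reaction last T days and be stored as k consecutive records.

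- If no day is counted twice, the segments sum to T and the reported mean is T/k.
- If the stop date of one record is also the start date of the next and both days count, the segments sum to T + k - 1 and the mean is (T + k - 1)/k. The SAP does not state the day-count convention for AESI duration, so both are shown.

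Example: stages of 5, 7 and 8 days.

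- True length: 5 + 7 + 8 = 20 days, group 16-29.
- Reported: 20/3 = 6.7 days, group 4-7.
- Reported with shared days: (20 + 2)/3 = 7.3 days, which falls between 4-7 and 8-15.

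Other assumed lengths, with the SAP group in brackets:

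| T (group) | T/2 | T/3 | (T+1)/2 | (T+2)/3 |
|---|---|---|---|---|
| 14 (8-15) | 7.0 (4-7) | 4.7 (4-7) | 7.5 (none) | 5.3 (4-7) |
| 20 (16-29) | 10.0 (8-15) | 6.7 (4-7) | 10.5 (8-15) | 7.3 (none) |
| 30 (>29) | 15.0 (8-15) | 10.0 (8-15) | 15.5 (none) | 10.7 (8-15) |
| 42 (>29) | 21.0 (16-29) | 14.0 (8-15) | 21.5 (16-29) | 14.7 (8-15) |

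Sharing boundary days raises the mean by (k - 1)/k, always less than one day.

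**Several reactions in one subject.** Let N true reactions with total length S be stored as M records. The true mean is S/N and the reported mean is S/M, so the ratio of reported to true is N/M. It equals 1/k only when N = 1.

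Example: the same 20-day reaction in three records, plus nine one-day reactions.

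- S = 20 + 9 = 29, N = 10, M = 3 + 9 = 12.
- True mean 29/10 = 2.9 days; reported mean 29/12 = 2.4 days.
- Ratio 10/12 = 0.83, a reduction of 17%, against 67% when the 20-day reaction stands alone.

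Even the correct mean of 2.9 days hides the 20-day reaction, which is a reason to report the longest episode as well.

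**The case against.** The strongest reply has four parts.

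**The term is undefined.** The programmers may treat an occurrence as a clinical episode and join records without saying so. That is possible, but neither document says it, and a prespecified plan should. The record-level reading remains an inference from the text.

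**Splitting is less common than it sounds.** The trigger is adverse event intensity, which Protocol 7.1.4 defines by how far the event interferes with daily activities. A wound that changes in appearance, or a site that moves on the separate 0-3 local tolerance scale, does not by that fact create a new record. Changes within a day are not split, and four of the ten duration groups for skin and hypersensitivity events lie below 24 hours. This stands, and it limits how many subjects are affected.

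**Other outputs are intact.** Incidence, severe, serious and withdrawal counts are per subject. Listings show every record, local tolerance is scored separately by investigator and subject, and skin AESIs are photographed until they resolve. This also stands, but none of these outputs restores the planned duration summary.

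**A careless repair would do harm.** Dosing is daily. Joining all adjacent-day records of one term would turn 30 separate one-day erythemas into a single 30-day episode. This stands, and it determines the form of the fix.

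A reader might also infer that the comparison is biased in favour of the patch. The documents do not support that: the same rules apply to both arms, and nothing gives the frequency of intensity changes in either.

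**Conclusion.** The point holds in a limited form. Read at record level, the SAP understates the duration of a reaction whose recorded intensity changes over more than a day. The reported mean is N/M of the true mean, which is about 1/k for a subject with one reaction in k stages. In the assumed example that is 6.7 days against 20, two groups too short.

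Two stronger readings should be avoided. It is not a general division by k, because other reactions in the same subject dilute the effect. Nor does a split reaction enter the duration summary as several short ones: the subject contributes one shortened average, and the separate records appear only in the data and listings.

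The effect is confined to the descriptive AESI duration summaries. The BMD analyses, incidence counts and maximum-severity tables are untouched. Its size in this trial, and any difference between arms, cannot be computed from the documents. The gaps between duration groups are a separate defect that arises from any averaging. Both are worth correcting because the repair is cheap and the output is a planned tolerability result.

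**What to change.** Amend SAP 4.6.2 as follows.

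1. **Define an episode.** Before computing duration, join consecutive records in the same subject when all three conditions hold: same preferred term; the next record starts on, or the day after, the previous stop date; and the recorded intensity differs. These are the marks of a record made by the protocol's split rule. Do not join adjacent-day records of the same intensity, which may be new reactions to successive doses.
2. **Duration.** Take it from first onset to last stop of the episode. The 20-day example then counts as 20 days.
3. **Longest episode.** Report each subject's longest episode beside the mean.
4. **Groups.** Make the longer groups contiguous, for example 2 to <4, 4 to <8, 8 to <16, 16 to <30 and ≥30 days. Whole-day values keep their present group.

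The cost is a few lines of SAP text and one data step. A few distinct reactions on adjacent days with different intensity may be joined; the listings still show the records as collected. If the change comes after SAP approval, SAP Section 1 already provides for identifying significant changes in Section 9.8 of the study report.
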